# 4.2.3.2.5. Global evaluation of therapy tolerability by the patient and the physician

Global evaluation of study drug tolerability should be made by the patient and Investigator according to the following scale:

Scores	Evaluation
0	Poor
1	Satisfactory
2	Good
3	Excellent

Evaluation of the study drug tolerability by the patient and the physician (points/scores) should be specified in the eCRF at Visits 2 or 3 (where applicable).

#### 4.2.3.2.6 Laboratory tests

The blood for analysis will be collected in the morning, in the fasted state (10–12 hours after the last meal) from the cubital vein by a disposable sterile syringe under aseptic conditions. Approximately 12 ml (1 tablespoonful) of blood will be collected at Visits 1 and 2 (or 3, where applicable).

Hematology (Hb, RBC, WBC, WBC differential, ESR) and biochemistry (total protein, ALT, AST, total bilirubin) will be conducted at the trial site laboratory. Pregnancy urine testusing test strips (immunochromatographic assay of beta-chorionic gonadotropin in the urine) must be performed for all women with the preserved childbearing potential at the screening visit.

#### 4.2.3.2.7 Electrocardiography

ECG will be performed at Visit 1 and Visit 2 or 3 (where applicable). ECG includes electrocardiogram tracing in 3 standard and 3 augmented leads (from the extremities), as well as 6 chest leads at rest in the

lying position. ECG will be interpreted by cardiologist, therapist, or functional diagnostics specialist.

# 4.2.4 Trial stages

# 4.2.4.1 Screening/randomization/therapy initiation (Visit 1)

Visit 1 is scheduled for Day 1. At this visit, the doctor evaluates the patient's eligibility for the trial. If no non-inclusion criteria are met, the patient undergoes randomization, is given the study drug/comparator drug and a patient's diary, and is instructed on the patient's diary completion requirements. Screening visit procedures:

- Signing of the Informed Consent Form;
- Demographic data (date of birth, sex, age);
- Measurement of weight and height;
- Anamnesis gathering;
- Records on the concomitant therapy;
- Evaluation of inclusion/non-inclusion criteria;
- Evaluation of the throat pain intensity according to VAS;
- Fill-in of TSS questionnaire by the Investigator;
- Physical examination (including oropharynx);
- Measurement of the main vital signs;
- Hematology;
- Biochemistry;
- Urine pregnancy test;
- 12-lead ECG;
- Evaluation of inclusion/non-inclusion criteria;
- Randomization;
- Dispensing of the study drugs;
- Provision with the patient's diaries and training on the fill-in rules;
- Initiation of therapy with the study drugs;
- Evaluation of adverse events (including based on results of the throat and pharynx examination).

# 4.2.4.2 Efficacy evaluation visit (Visit 2, Day 4)

Visit 2 is conducted on Day 4; the patient must visit the trial site in the fasted state and bring the filled-in diary and unused drug.

If Group B patients (ANTI-ANGIN® FORMULA) did not meet recovery criteria (total  $TSS \le 2$ ) at Visit 2 (Day 4), they will require continuation of the therapy, and some procedures for those patients will be transferred for the next day (Visit 3, Day 5), see below. The patients will keep their diaries and the unused drugs.

Visit 2 procedures for the both groups:

- Collection of complaints, actualization of anamnesis;
- Records on the concomitant therapy;
- Physical examination (including oropharynx);
- Measurement of the main vital signs;
- Evaluation of adverse events (including based on results of the throat and pharynx examination);
- Evaluation of exclusion criteria;
- Compliance evaluation (diary completion, administration of the study drugs).

# Visit 2 procedures for Group A patients (Angal) and Group B (ANTI-ANGIN® FORMULA) who achieved recovery criteria (total TSS $\leq$ 2):

- Hematology;
- Biochemistry;
- 12-lead ECG;
- Global evaluation of treatment tolerability during the trial by the physician and the patient;
- Return of the unused study drug;
- Return of the patient's diary;

# 4.2.4.3 Trial completion visit for Group B patients (Visit 3, Day 5)

This visit is for Group B patients only (ANTI-ANGIN® FORMULA) who did not achieve the recovery criteria (total TSS  $\leq$  2) at Visit 2 (Day 4)

Visit 3 is conducted on Day 5; the patient must visit the trial site in the fasted state and bring the filled-in diary and unused drug.

# Visit 3 procedures:

- Collection of complaints, actualization of anamnesis;
- Records on the concomitant therapy;
- Physical examination (including oropharynx);
- Measurement of the main vital signs;
- Evaluation of adverse events (including based on results of the throat and pharynx examination);
- Evaluation of exclusion criteria;
- Return of the unused study drug;
- Return of the patient's diary;
- Compliance evaluation (diary completion, administration of the study drugs).
- Hematology;
- Biochemistry;
- 12-lead ECG;

- Protocol No. TE 004 ANG LOZ
  - Global evaluation of treatment tolerability during the trial by the physician and the patient.

# 4.2.4.4 A follow-up visit (Visit 4)

A follow-up visit shall be conducted by phone to find out about the patient's state and any AEs. A visit 2 days after the therapy completion visit (e.g., on Day 6 or 7, depending on the arm and therapy duration).

Follow-up visit procedures (by phone):

• Evaluation of adverse events (without the throat and pharynx examination).

In case of adverse events, the patient might be invited to visit the trial site.

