# 1. Protocol synopsis

Trial title	A Prospective, Multicenter, Open, Randomized, Parallel Clinical Trial for Comparative Assessment of Efficacy and Safety of Angal, Lozenges [Menthol], 1  mg + 5  mg (Sandoz d.d., Slovenia), and ANTI-ANGIN ® FORMULA, Lozenges, 0.2  mg + 2  mg + 50  mg (OOO Valeant, Russia) in Treatment of Patients with Uncomplicated Acute Infectious and Inflammatory Diseases of the Pharynx Accompanied by a Sore Throat
Trial code	TE_004_ANG_LOZ
Sponsor	ZAO Sandoz
Study drug	Angal, lozenges [menthol], containing 1 mg of lidocaine hydrochloride and 5 mg of chlorhexidine dihydrochloride
Reference drug	ANTI-ANGIN ® FORMULA, lozenges, containing 0.2 mg of tetracaine hydrochloride, 2 mg of chlorhexidine diacetate, and 50 mg of ascorbic acid
Clinical trial phase	
Trial population	Up to 280 patients are planned to be included (randomized) into the trial (140 patients in every treatment arm) with probable withdrawal of not more than 10% patients during the trial. A minimal number of patients required for the statistical analysis is 256 (128 patients in every treatment arm) provided that they completed the trial according to the protocol.
Scheduled trial duration	Not more than 7 days: Screening/randomization/initiation of trial therapy: Day 1. Therapy duration: up to 5 days depending on the trial arm. A follow-up visit (on the phone): 2 days after the last scheduled visit to the trial site. Total enrollment duration: 8 months.
The number of trial sites	up to 20

Trial objective	This trial has been designed to evaluate the non-inferior therapeutic efficacy and safety of the study drug Angal, lozenges [menthol] 1 mg + 5 mg (Sandoz d.d., Slovenia), comparing to ANTI-ANGIN ® FORMULA, lozenges, 0.2 mg + 2 mg + 50 mg (OOO Valeant, Russia), in treatment of patients with uncomplicated acute infectious and inflammatory diseases of the pharynx accompanied by a sore throat.

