#### Secondary goals:

- Assessment of safety of Angal, lozenges [menthol], 1 mg + 5 mg (Sandoz d.d., Slovenia) administration of 1 lozenge with a not less than 2-hour interval, up to 6–10 times per day, for 4 days or until full recovery (whichever occurs first during 4 days of therapy), compared to ANTI-ANGIN® FORMULA, lozenges, 0.2 mg + 2 mg + 50 mg (OOO Valeant, Russia)—administration of 1 lozenge with a not less than 2-hour interval, up to 6 lozenges per day, for 5 days or until full recovery (whichever occurs first during 5 days of therapy) in the treatment of patients with uncomplicated acute Infectious and inflammatory diseases of the pharynx accompanied by a sore throat.
- Evaluation of adverse events (AEs) in the trial arms.
- The AEs rate comparison between the trial arms.

S. SANDOZ

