# 4.5 Expected duration of the subjects' participation in the trial

Screening period: 1 day;

Treatment period: up to 5 days (including the screening/randomization day);

Follow-up period: up to 2 days.

A maximum duration of each subject's participation: 7 days. A minimum duration of each subject's participation: 6 days (depending on the arm).

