# 4.1.4 Safety and tolerability analysis

AEs incidence will be compared between the trial arms using Pearson's chi-squared test. In case of significant changes, a relative risk will be calculated (with 95% CI).

A tolerability level for every group will be calculated based on the AEs incidence and nature (in accordance with Section 2.3 of this Plan).

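### Adverse events are collected one day longer, with one extra on-site clinical assessment, only in unrecovered comparator patients, and the crude between-arm AE comparison does not allow for it; the effect is small

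*Protocol*

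**What the plan says.** The synopsis places the follow-up call "2 days after the last scheduled visit to the trial site". Protocol 4.2.4.4 and SAP 3.8.4 tie it to the therapy completion visit and put it "on Day 6 or 7, depending on the arm and therapy duration". Protocol 4.5 agrees: "A minimum duration of each subject's participation: 6 days (depending on the arm"), with a maximum of 7 days.

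Protocol 4.2.4.3 describes the Day 5 visit: "This visit is for Group B patients only", namely those whose total TSS was still above 2 on Day 4. Its procedures include "Evaluation of adverse events (including based on results of the throat and pharynx examination"), together with complaints and a physical examination, all of which were also done at Visit 2. For the same patients, Protocol 4.2.4.2 says that "some procedures for those patients will be transferred for the next day (Visit 3, Day 5"). Sections 4.2.4.2 and 4.2.4.3 show that these are hematology, biochemistry, ECG, the tolerability rating, and the return of drug and diary.

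The secondary goals in Protocol 3.2 include: "The AEs rate comparison between the trial arms". SAP 4.1.4 states that "AEs incidence will be compared between the trial arms" with a Pearson chi-squared test, whereas Protocol 9.1.4 names Fisher's exact test. SAP Table 23 reports n/N (%) with a p-value. Neither document sets a common cut-off day, a rate per person-day or a sensitivity analysis for unequal follow-up.

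**The concern.** A crude proportion of patients with an AE rises with the length of observation and with the number of times patients are examined and asked. Both can be greater in one arm only. A Group A patient who is still ill on Day 4 has no Day 5 visit and is called on Day 6; the same patient in Group B is seen on Day 5 and called on Day 7. The difference depends on a post-randomization outcome (non-recovery), and it falls on the patients with the most symptoms to report, in an open-label trial. Its direction is fixed by the schedule: with equal true daily risk, Angal looks slightly safer than it is relative to the comparator. What is at stake is the interpretation of a stated secondary goal, in a trial whose objective also mentions non-inferior safety.

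**Working it through.** **1. Windows from the visit schedule.**
- Group A, recovered or not: Visit 2 on Day 4, plus 2 = Day 6.
- Group B, recovered at Day 4: 4 + 2 = Day 6.
- Group B, unrecovered at Day 4: Visit 3 on Day 5, plus 2 = Day 7.

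These reproduce the 6-day minimum and 7-day maximum in Protocol 4.5. For an unrecovered Group B patient the window is 7/6 = 1.167 times that of a Group A patient. Scheduled AE contacts after Visit 1 are 3 against 2, and on-site ones 2 against 1.

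**2. What Visit 3 adds.** History, physical and throat examination and AE questioning are done at both Visit 2 and Visit 3, so they are extra. Laboratory tests, ECG and the tolerability rating are done once in either case. Vital signs are unclear: Protocol 4.2.4.2 lists them at Visit 2 for both groups, but the visit schedule table marks them there as only for Group A and recovered Group B. Unrecovered Group B patients also keep the diary for Day 5, while Group A returns it on Day 4.

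**3. Mean window in Group B.** Let u be the share of Group B unrecovered at Day 4. The documents do not give u, so I take 0.20 to 0.50. The value 0.37 (= 1 − 0.63) is only a proxy, from the 63% assumed free of sore throat in Protocol 9.2, which is a different criterion from total TSS ≤ 2. The mean window is 6 + u days:
- u = 0.20: 6.20/6 = 1.033
- u = 0.37: 6.37/6 = 1.062
- u = 0.50: 6.50/6 = 1.083

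**4. Effect on incidence.** Assume the same constant daily hazard h in both arms. If p is the incidence over 6 days, then h = −ln(1 − p)/6, and Group B incidence = (1 − u)·p + u·(1 − exp(−7h)).

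Example, p = 10%: h = 0.10536/6 = 0.01756; 1 − exp(−0.12292) = 11.57%. With u = 0.20, 0.8 × 10% + 0.2 × 11.57% = 10.31%.

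| Group A | Group B, u = 0.20 | u = 0.37 | u = 0.50 |
|---|---|---|---|
| 5% | 5.16% | 5.30% | 5.40% |
| 10% | 10.31% | 10.58% | 10.78% |
| 20% | 20.58% | 21.08% | 21.46% |

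The excess is 0.16 to 1.46 percentage points, a risk ratio of about 1.03 to 1.08. With 140 patients per arm and p = 10%, that is 140 × 0.0031 = 0.4 to 140 × 0.0078 = 1.1 patients. Detections due to the extra examination and diary day are not in this model and cannot be quantified from the documents.

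**5. Effect on the test.** With 140 per arm, a two-sided 5% test and a normal approximation, the chance of a falsely significant result against Group B rises from 2.5% to 2.9% (p = 5%, u = 0.20) and up to 4.9% (p = 20%, u = 0.50).

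**6. After the change.** With the call on Day 7 for everyone the window ratio is 7/7 = 1.00. The Day 5 assessment still exists in Group B only.

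**The case against.** The strongest reply is that the windows are already equal relative to treatment: both arms are called two days after their last scheduled site visit. Group B's extra day exists because its regimen runs up to 5 days against 4, and the secondary goal compares exactly these two regimens. Events on or after a fifth treatment day may belong to the comparator. This stands in part. Some of any excess could be real exposure, and a crude n/N cannot separate exposure from detection. It does not remove the point, because the test compares cumulative incidence, for which total observation matters, and unrecovered Group A patients are not observed on Day 7 at all.

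Two further replies stand. The effect is small. And no decision depends on it: SAP section 4 confines the non-inferiority conclusion to the primary parameter and treats safety variables as of research interest, and there is no safety margin.

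A reader might infer that Group B gets more laboratory and ECG surveillance. The documents do not support that; those tests are postponed by a day, not repeated. A reader might also infer that a Day 6 onset cut-off would settle the matter by SAP wording alone. It would not: it leaves unrecovered Group B patients one day after their last site visit against two in Group A, drops comparator events from the test, and still counts whatever the Day 5 examination finds.

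**Conclusion.** The asymmetry is real and its direction is fixed by the design: AE observation is longer, with one more clinical assessment, only in unrecovered comparator patients, and the planned crude comparison makes no allowance for it. For an assumed unrecovered share of 20–50%, equal constant daily risk and a 6-day AE incidence of 5–20%, the size is about 3–8% more observation time and 0.2–1.5 percentage points. Even if every Group B patient were unrecovered, the window ratio could not exceed 1.167.

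A stronger reading, that the safety comparison is materially biased in favour of Angal or that a safety conclusion is undermined, is not supported. The effect is small, part of any excess may be due to the extra treatment day, and the plan has no formal safety hypothesis. This is a low-priority improvement.

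**What to change.** - In Protocol 4.2.4.4 and SAP 3.8.4, place the Visit 4 call on Day 7 for all patients in both arms, and align the synopsis, the visit schedule table and Protocol 4.5.
- In Protocol 9.1.4 and SAP 4.1.4, compare AE incidence over Days 1–7, and name the same test in both documents.
- Because the Day 5 examination remains in Group B only, add a sensitivity comparison of AEs with onset up to Visit 2 (Day 4), before the schedules diverge. Also show AEs per person-day by arm.
- Confirm that the eCRF records AE onset dates. The protocol's list of AE descriptors names duration but not onset.
- Do not make a Day 6 cut-off the main analysis.

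Cost: the call comes one day later for most patients, and minimum participation becomes 7 days, within the existing maximum. Patients whose last site visit is Day 4 would then be followed for three days after it, against two for those seen on Day 5, but no events are dropped. The protocol wording must be amended; Protocol 11.2 requires approval before an amendment takes effect and classes changes that may influence trial or statistical methods as significant. No treatment rule changes. If the calls have already been made, the two supplementary analyses can still be done.

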# 4.2.4.5 Unscheduled visits

The unscheduled visits will be conducted when necessary, e.g., in case of the index disease deterioration, AEs, or the study drug (Angal or ANTI-ANGIN® FORMULA) intolerability.

Every unscheduled visit, irrespective of its cause, must include the procedures listed below with completion of the relevant eCRF pages (Unscheduled Visit):

- Physical examination (including topical examination);
- TSS evaluation;
- Measurement of the main vital signs (blood pressure, heart rate, breathing rate, body temperature);
- 12-lead ECG (if it has not been done for the last 12 hours);
- Evaluation of adverse events;
- Evaluation of the concomitant therapy.

Other diagnostic and treatment procedures may be conducted depending on clinical situation and upon the Investigator's decision.

Taking into account frequency of visits, unscheduled visits may be conducted on the same days as scheduled ones but in a different time (e.g., in case of worsening the patient may visit the center in afternoon). All procedures for the scheduled visits are identical for the both arms at every trial stage, except for the Group B patients who, if the recovery criteria (total TSS  $\leq$  2) are not met at Visit 2 (Day 4), should continue the trial therapy and visit the trial site for scheduled Visit 3 Day 5).

#### 4.2.4.6 Visit of premature discontinuation of the trial

Visit 2 procedures will be applied for the visit of premature discontinuation.

#### 4.3 Subjectivity minimization/elimination measures

#### 4.3.1 Randomization

This will be an open, randomized trial. Every screened patient will be assigned with an individual registration number containing the initials (name, patronymic, surname) and a participant's number assigned to every new screened patient in a three-digit format (001, 002, etc.). The patients who meet the inclusion criteria at the screening visit will be randomized to a study drug group or a comparator drug group using the envelope method. For the purpose of randomization, a list of randomization numbers for the envelops will be generated, every number will correspond to a study drug group or a comparator drug group.

# 4.3.2 Blinding methods

This trial will be conducted without blinding (an open trial).

# 4.4 Description of the drugs used in the trial

#### 4.4.1 Dosage form

**Study drug**: Angal, lozenges [menthol], 1 mg + 5 mg. White to off-white, round, slightly mottled lozenge.

**Comparator drug**: ANTI-ANGIN® FORMULA, lozenges, 0.2 mg + 2 mg + 50 mg. Lozenges: flat, round, with beveled edges and rough surface, of pink to pinkish-red color, with a specific odor. Color non-uniformity, presence of air bubbles in a high-boiled sugar mass, and insignificant edge irregularity are allowed.

# 4.4.2 Packaging

**Study drug**: Aluminum and PVC/PCTFE foil blister. 24 lozenges (2×12) in a carton pack. **Comparator drug**: Lozenges. 10 lozenges in AL-PVC blister; 3 blisters in a carton pack.

#### 4.4.3 Labeling of the study drugs

As this is an open trial, the trial site will be provided with the packed products from the series commercially available in the EU (study drug) and Russia (comparator drug). Every carton box with the drugs will contain a self-adhesive label with the data listed below:

• "For clinical trials only";

- A protocol number;
- Title, address, and phone number of the trial site;
- Title, address, and phone number of the trial Sponsor;
- A field for a patient's randomization number.

The label should not overlap the drug name, active substances, and their strength, shelf life, manufacturer's name.

At the screening visit, every patient in the study drug group will be given 2 packages of Angal (48 lozenges), and every patient in the comparator drug group will be given 1 package of ANTI-ANGIN® FORMULA (30 lozenges). The dispensed amounts are sufficient for completion the trial according to the protocol. An excess of the drugs is envisaged for the cases of loss of some lozenges.

# 4.4.4 Strength and dosage regimen of the study drugs

Angal, lozenges [menthol], 1 mg + 5 mg (Sandoz d.d., Slovenia), the study drug, will be used according to Prescribing Information, 1 lozenge with a not less than 2-hour interval, up to 6–10 times per day, for 4 days or until full recovery (total TSS  $\leq 2$ ) (whichever occurs first during 4 days of therapy). A single dose of Angal is 1 lozenge. The lozenges are intended for full dissolution in the oral cavity. One lozenge is slowly disintegrating in the mouth.

ANTI-ANGIN® FORMULA, lozenges, 0.2 mg + 2 mg + 50 mg (OOO Valeant, Russia), the comparator drug, will be used according to Prescribing Information, 1 lozenge with a not less than 2-hour interval, up to 6 lozenges per day, for 5 days or until full recovery (total TSS  $\leq 2$ ) (whichever occurs first during 5 days of therapy). One dose of ANTI-ANGIN® FORMULA is 1 lozenge. The lozenges are intended for full dissolution in the oral cavity. One lozenge is slowly disintegrating in the mouth.

# 4.5 Expected duration of the subjects' participation in the trial

Screening period: 1 day;

Treatment period: up to 5 days (including the screening/randomization day);

Follow-up period: up to 2 days.

A maximum duration of each subject's participation: 7 days. A minimum duration of each subject's participation: 6 days (depending on the arm).

#### 4.6 Description of rules for termination of the trial parts or the trial as a whole

The trial may be terminated on the following grounds:

- 1. Upon the Sponsor's initiative: availability of new toxicological or pharmacological data, or data on SAE which require re-consideration of the previous evaluation of the benefit/risk ratio.
- 2. Upon the Sponsor's initiative: AEs incidence or severity require the trial termination.
- 3. Upon the Sponsor's initiative: other reasons including administrative ones.
- 4. Upon the decision of the regulatory authorities.

The trial may be terminated at a specific trial site in case the patients enrollment or data quality are unsatisfactory, or it is reasonable to assume a breach of GCP and/or Declaration of Helsinki, or other serious protocol deviations.

In case of early termination of the trial, the Sponsor must inform the trial site personnel as well as regulatory authorities with indication of the reason thereof. The rules for trial termination for every participant are described in Section 5.3.

